| | 13.4 | Exclusion of Women, Minorities, and Children (Special Populations) | |
| | 13.5 | Subject Confidentiality | |
| 14 | | Handling and Record Keeping | 33 |
| | 14.1 | Data Management Responsibilities | |
| | 14.2 | Data Capture Methods | |
| | 14.3 | Study Records Retention | |
| | 14.4 | Protocol Deviations | |
| 15 | Public | cation Policy | 35 |

| MSG 15 Mayne Endemic Mycoses Study | Version 5.0 19 August 2020 |
|------------------------------------|-------------------------------|
| 16 Literature References | 36 |
| Appendix A: Schedule of Events | 38 |
| | |
| | |
| | |

LIST OF ABBREVIATIONS

AE Adverse Event/Adverse Experience

CFR Code of Federal Regulations

CIOMS Council for International Organizations of Medical Sciences

CONSORT Consolidated Standards of Reporting Trials

CFR Code of Federal Regulations

CRF Case Report Form

CRO Contract Research Organization

DCC Data Coordinating Center
DRC Data Review Committee
eCRF Electronic Case Report Form
FDA Food and Drug Administration
FWA Federal Wide Assurance
GCP Good Clinical Practice

HIPAA Health Insurance Portability and Accountability Act

IB Investigator's Brochure ICF Informed Consent Form

ICH International Conference on Harmonisation

ICMJE International Committee of Medical Journal Editors

IDE Investigational Device Exemption

IEC Independent or Institutional Ethics Committee

IND Investigational New Drug Application

IFI Invasive fungal infection
IRB Institutional Review Board
ISM Independent Safety Monitor

JAMA Journal of the American Medical Association

MedDRA ® Medical Dictionary for Regulatory Activities

MOP Manual of Procedures

N Number (typically refers to subjects)
NCI National Cancer Institute, NIH, DHHS

NDA New Drug Application

NEJM New England Journal of Medicine
OHRP Office for Human Research Protections
OHSR Office for Human Subjects Research

ORA Office of Regulatory Affairs, DMID, NIAID, NIH, DHHS

PHI Protected Health Information

PI Principal Investigator
PK Pharmacokinetics
QA Quality Assurance
QC Quality Control
QOL Quality of Life

SAE Serious Adverse Event/Serious Adverse Experience

SF-12 Short Form 12 Version 2

SOP Standard Operating Procedure

US United States

WHO World Health Organization

PROTOCOL SUMMARY

Title: SUBA-itraconazole versus conventional itraconazole in the

treatment of endemic mycoses: an open-label comparative trial

Phase: IIb

Population: 80 adults infected with one of the endemic mycoses living in the United

States, Canada and Central/South America (Approximately: 40 Histoplasmosis, 20 Coccidioidomycosis, 20 other endemic mycoses)

Number of Sites: Approximately 20 total sites in US, Canada, and Central/South

America

Study Duration: This study is estimated to be opened for 18 months after initiation (12

month patient accrual, 6 month treatment period).

Subject Each participant will be enrolled in the study for 180 days

Participation

Objectives:

The objectives of this study are to compare PK, tolerance, safety, and efficacy of SUBA-Itraconazole study drug versus conventional itraconazole in a randomized open-label trial followed by a second stage of continuing open-label study drug.

Stage I - Randomized, Open-Label, Parallel Group

Primary Objective

- PK at Day 14
- Tolerability at Day 42

Secondary Objective

- PK at Day 7
- PK at Day 42
- Efficacy by Day 42
- Safety by Day 42
- QOL (including hospital/ICU visits) Assessments by Day 42

Stage II - Open-Label Extension

Primary Objective

- Efficacy by Day 180
- Tolerability by Day 180

Secondary Objective

- Safety by 180
- QOL (including hospital/ICU visits) Assessments by Day 180

Description of Study Design:

[figure not shown]
This is a prospective, multi-center, randomized, open-label parallel arm study involving patients with proven or probable invasive endemic fungal infection to ascertain the pharmacokinetics, safety, efficacy, tolerability and health economics of oral SUBA-itraconazole compared to conventional itraconazole. Patients will receive randomized open-label study drug (SUBA-itraconazole or conventional itraconazole) over a 42 day period and then continue therapy until Day 180 or earlier if Principal Investigator determines discontinuation of therapy is safe. Patients will be stratified based on clinically reported infection with the human immunodeficiency virus (HIV).

The study sample size will be 80 evaluable patients – target enrollment (three groups: approximately 40 histoplasmosis, 20 coccidioidomycosis, 20 other endemic fungal infections).

Estimated Time to Complete Enrollment

12 Months

Schematic of Study Design:

2.1 Background Information

The endemic mycoses are a diverse group of diseases that share several characteristics. They are able to cause disease in otherwise healthy hosts, each pathogen occupies a specific ecologic niche in the environment, are located within a specific geographic region, and exhibit temperature dimorphism – existing as yeasts in the host and molds in the environment [1].

These dimorphic fungi consist of numerous species, however *Histoplasma*, *Coccidioides*, *Paracoccidioides*, *Blastomyces*, *Sporothrix*, and *Talaromyces* (*Penicillium marneffei*) represent the most commonly encountered infections in clinical care. *Histoplasma* spp. are common throughout the Mississippi, Ohio, and St. Lawrence River valleys, the Caribbean, parts of Central and South America, Africa and Asia [2]; *Coccidioides* within the southwestern U.S., and parts of central and South America [3]; *Paracoccidioides* within Central and South America [4]; *Blastomyces* within the Mississippi and Ohio River basins, St Lawrence Seaway, and several Canadian provinces with sporadic cases in Africa, Central and South America [5]; *Sporothrix schenckii* is found worldwide [6]; and *Talaromyces* in Southeast Asia, India, Southern China and Hong Kong [7].

However, the range of the endemic mycoses has been recently questioned and reports describing these pathogens outside of their "known" endemic regions have emerged with increased frequency over the last few years [8-10]. These reports suggest the true incidence and distribution of these fungi may be far greater than previously recognized and thus a much larger population of patients is continually exposed to these pathogens.

Exposure is largely unavoidable for those residing or visiting the endemic regions. Following inhalation these organisms are ingested by pulmonary macrophages yet they frequently are able to survive ingestion and escape, replicate, and thereafter cause disease with ensuing host morbidity and mortality.

The treatment of the endemic mycoses can be difficult for both clinicians and patients. The majority of the endemic mycoses require long courses of antifungal treatment - with courses frequently requiring months to life-long suppressive therapy. Initial therapy for severe disease has traditionally consisted of an amphotericin B formulation and prolonged therapy is limited by the inherent toxicity of polyenes. Following improvement with an amphotericin B formulation, a triazole is prescribed for continuing therapy, usually for a minimum of 6-12 months, depending on the infection.

Currently available agents are limited in the treatment of the endemic fungi by toxicity, poor oral bioavailability [11] or resistance. Fluconazole is widely available yet has limited activity against several of the endemic mycoses including histoplasmosis [12], while in others such as coccidioidomycosis treatment at high doses (> 800 mg/day) is

required, limiting patient tolerability. Voriconazole has been associated with cutaneous malignancy, photosensitivity [13], fluorosis [14], hepatotoxicity, inter-patient pharmacokinetic variability, and has limited activity against *Sporothrix* sp. Itraconazole exhibits variable absorption due to numerous intrinsic and extrinsic factors. In addition, food/acidity requirements are difficult for patients to maintain long-term. Posaconazole solution similarly exhibits dietary requirements and absorption concerns that limit patient compliance and bioavailability [15].

SUBA-itraconazole with twice-daily oral dosing options have improved pharmacokinetics and lack of food/acidity requirements [16].

2.2 Rationale

The availability of SUBA-itraconazole (65 mg capsules) with twice-daily dosing options with improved pharmacokinetics and lack of food/acidity requirements offers a substantial opportunity to improve the treatment of patients with endemic mycoses [16].

2.3 Potential Risks and Benefits

2.3.1 Potential Risks

All medical treatments have the potential of causing undesirable effects. For this reason, the study is performed under carefully controlled conditions.

Common side effects reported to date in patients taking conventional itraconazole (reported in 1-10% of the patients):

- Vomiting
- Diarrhea
- Abdominal pain
- Anorexia
- Edema
- Fatigue
- Fever
- Malaise
- Rash*
- Pruritus

- Headache
- Dizziness
- Libido Decreased
- Somnolence
- Hypertension
- Hypokalemia
- Albuminuria
- Hepatic Function Abnormal
- Impotence

Nausea (11%) is a common side effect (reported in more than 10% of patients) associated with other marketed azoles that may or may not be associated with SUBA-Itraconazole.

Common side effects that were reported in less than 10% of patients taking other marketed azoles (fluconazole, voriconazole, itraconazole, ketoconazole, posaconazole, isavuconazole) were:

- Dizziness
- Chest pain
- Flatulence
- Sleeplessness
- Liver function test abnormalities
- Renal insufficiency

- Trouble Breathing
- Digestion problems
- Tremors
- Asthenia (weakness)
- Cardiovascular problems such as tachycardia or arrhythmia
- Vision disturbances

3 OBJECTIVES

3.1 Study Objectives

The purpose of this study is to compare safety, tolerance, PK, efficacy and cost effectiveness of SUBA-Itraconazole to conventional itraconazole in a randomized, open-label, parallel group trial followed by a second stage (open-label extension) where participants will continue open-label study drug.

3.2 Study Outcome Measures

3.2.1 Primary and Secondary Outcome Measures – Stage I (Open-Label Parallel Group)

Primary Outcomes

- PK at Day 14
- Tolerability at Day 42

Secondary Outcomes

- PK at Day 7
- PK at Day 42
- Efficacy by Day 42
- Safety by Day 42
- QOL (including hospital/ICU visits) Assessments by Day 42

3.2.2 Primary and Secondary Outcome Measures - Stage II (Open-Label Extension)

Primary Outcomes

- Efficacy by Day 180
- Tolerability by Day 180

Secondary Outcomes

- Safety by 180
- QOL (including hospital/ICU visits) Assessments by Day 180

4 STUDY DESIGN

This is a prospective, multi-center, randomized, open-label parallel arm study involving patients with proven or probable invasive endemic fungal infection to ascertain the pharmacokinetics, safety, efficacy, and tolerability of oral SUBA-itraconazole or itraconazole. Patients will receive randomized open-label study drug (either SUBA-itraconazole 65 mg twice daily or itraconazole 100 mg twice daily) over a 42-day period and then continue on their assigned open-label therapy until day 180.

The study sample size will be 80 evaluable patients – target enrollment to include approximately 40 histoplasmosis, 20 coccidioidomycosis, and 20 other endemic fungal infections.

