5.3 Treatment Assignment Procedures

5.3.1 Randomization Procedures

Stratified randomization will be used to assign qualifying participants to either conventional itraconazole or SUBA-itraconazole and dosed according to HIV status (positive or negative by clinical self-report) (Section 6.2).

Randomization procedures are described in the Manual of Procedures.

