6.1.2 Formulation, Packaging, and Labeling

SUBA-itraconazole Investigator Brochure and conventional itraconazole package insert are provided as separate documents. The conventional itraconazole package insert is also located at:

http://www.janssen.com/us/sites/www janssen com usa/files/products-documents/pi-sporanoxcapsules.pdf)

SUBA-itraconazole study drug will consist of 65 mg capsules.

Conventional itraconazole will consist of 100 mg capsules.

Study drug will be packaged and labeled according to labeling instructions in the Manual of Procedures. Patients will be dispensed study drug by the site with sufficient amount of drug to last through the next study visit plus 5 days. Investigators at each site may determine if the site pharmacy may ship study drug to the participants' homes when clinic visits are not recommended or possible.

Patient initials, Study ID, and date will be recorded on dispensed study record. Documentation of dispensing, including identification of who dispensed the study drug, will be recorded in both the drug accountability log and the patient source documents.

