6.2 Dosage, Preparation and Administration of Study Intervention/Investigational Product

Study participants will be randomized to receive either open-label SUBA-Itraconazole or conventional itraconazole. Each treatment arm will be dosed as follows:

Arm A: Open-Label SUBA-itraconazole 65 mg Capsules – administered with food

Stage 1

- Day 1 3: two 65 mg capsules, three times daily
- Day 4 42: two 65 mg capsules, twice daily

Stage 2:

Day 43 – 180: two 65 mg capsules, twice daily.

Arm B: Conventional Itraconazole 100 mg Capsules – administered with food Stage 1:

- Day 1 3: two 100 mg capsules, three times daily
- Day 4 42: two 100 mg capsules, twice daily

Stage 2:

Day 43 – 180: two 100 mg capsules, twice daily).

Based on standard of care for invasive endemic fungal infection, some participants will be prescribed conventional itraconazole (non-study drug) after Day 180 for up to a year or beyond, as prescribed by their physician. Information for discounted itraconazole will be provided at the end of the study to help defray costs.

[figure not shown]

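### Sections 4 and 6.2 state different study doses in both arms, threefold apart on Days 1-3 and twofold from Day 4, and the HIV dosing wording in 5.3.1 has no counterpart in the available text of 6.2

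*Combined protocol and SAP*

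**What the plan says.** Section 4 (Study Design) describes randomized treatment as "either SUBA-itraconazole 65 mg twice daily or itraconazole 100 mg twice daily" over 42 days, followed by the assigned therapy to Day 180. It mentions no different regimen for the first days.

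Section 6.1.2 gives one strength per product: "SUBA-itraconazole study drug will consist of 65 mg capsules" and "Conventional itraconazole will consist of 100 mg capsules".

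Section 6.2 (Dosage, Preparation and Administration) gives a day-by-day schedule:

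- **SUBA-itraconazole:** "two 65 mg capsules, three times daily" on Days 1-3, then "two 65 mg capsules, twice daily" on Days 4-42 and again on Days 43-180.
- **Conventional itraconazole:** "two 100 mg capsules, three times daily" on Days 1-3, then "two 100 mg capsules, twice daily" for the same later periods.

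Section 5.3.1 (Randomization Procedures) says participants are "dosed according to HIV status (positive or negative by clinical self-report) (Section 6.2"). The Protocol Summary uses HIV status only as a stratification factor.

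**The concern.** Section 4 states an amount and a frequency, which is a dose. At the strengths in Section 6.1.2 it means one capsule twice daily from Day 1. Section 6.2 doubles the capsules per dose throughout and adds a third daily dose on Days 1-3. The available text contains no clause saying which section governs.

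The first thing at stake is participant safety, because the protocol states two regimens for the same drugs that differ two- to threefold. Several trial elements also depend on absolute dose:

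- the Day 14 trough and Day 42 tolerability, both primary in Stage I;
- the time to exceed the fixed 500 mcg/L level in Section 10.3;
- the concentration limits in Section 6.3 that prompt a dose change;
- the quantity dispensed to the next visit plus 5 days, and compliance judged from returned drug;
- the Day 42 capsule count, listed as a health economic endpoint.

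The HIV wording raises a second, smaller question. If dosing really depends on HIV status, the available text of Section 6.2 does not say how. If it does not, Section 5.3.1 is misworded.

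**Working it through.** **Inputs.** Strengths of 65 mg and 100 mg (Section 6.1.2). Section 4: one capsule, twice daily, from Day 1. Section 6.2: two capsules, three times daily on Days 1-3 and twice daily from Day 4. Dose modifications under Section 6.3 are ignored. The protocol gives no daily or cumulative totals, so there is no stated figure to reproduce. The 77% power in Section 10.2 plays no part in this check.

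**Daily dose** = capsules per dose × strength × doses per day.

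| Arm and period | Section 4 | Section 6.2 | Ratio |
|---|---|---|---|
| SUBA, Days 1-3 | 1 × 65 × 2 = 130 mg | 2 × 65 × 3 = 390 mg | 3.0 |
| Conventional, Days 1-3 | 1 × 100 × 2 = 200 mg | 2 × 100 × 3 = 600 mg | 3.0 |
| SUBA, from Day 4 | 130 mg | 2 × 65 × 2 = 260 mg | 2.0 |
| Conventional, from Day 4 | 200 mg | 2 × 100 × 2 = 400 mg | 2.0 |

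**Planned exposure before the Day 14 sample.** Section 10.3 makes this a trough taken before the morning dose, so the last full dosing day is nominally Day 13.

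- Section 4: 13 × 2 = 26 capsules, or 26 × 65 = 1,690 mg SUBA and 26 × 100 = 2,600 mg conventional.
- Section 6.2: 3 × 6 + 10 × 4 = 58 capsules, or 58 × 65 = 3,770 mg SUBA and 58 × 100 = 5,800 mg conventional.
- Ratio: 58 / 26 = 2.23.

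The ±3-day visit window changes little. Sampling on Day 11 (10 full days) gives (18 + 7 × 4) / 20 = 46 / 20 = 2.30. Sampling on Day 17 (16 full days) gives (18 + 13 × 4) / 32 = 70 / 32 = 2.19.

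**Planned exposure through Day 42.**

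- Section 4: 42 × 2 = 84 capsules, or 5,460 mg SUBA and 8,400 mg conventional.
- Section 6.2: 3 × 6 + 39 × 4 = 174 capsules, or 11,310 mg SUBA and 17,400 mg conventional.
- Ratio: 174 / 84 = 2.07.

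**Between arms.** SUBA to conventional in mg is 130/200 = 260/400 = 390/600 = 0.65. Planned capsule counts are equal across arms under either section.

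**HIV wording.** Section 5.3.1 ties dosing to HIV status and points to Section 6.2. The available text of 6.2 sets the dose by arm and study day and does not mention HIV. The Protocol Summary mentions HIV only for stratification.

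**The case against.** The strongest reply is that this is a drafting slip with little practical effect. Section 4 is a design overview, whereas Section 6.2 is the dosing section, is far more detailed, and is where Section 5.3.1 sends the reader. Elsewhere the protocol identifies the products by capsule strength, so Section 4 may be shorthand that lost the word for capsules. Labelling instructions are in the Manual of Procedures, which is not available here, and nothing shows that any site has misdosed. The arms keep the same milligram ratio, and the Day 42 capsule count is observed, so the text conflict does not change how it is measured.

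Much of this stands. A slip is likely, the safety risk is potential rather than demonstrated, and no bias in the randomized comparison is claimed. It does not remove the conflict. Greater detail and a cross-reference are not a rule of precedence. The shorthand reading does not explain why Section 4 has no separate Days 1-3 regimen. Section 6.3 permits changes from an assigned regimen, but what is unclear is the assigned regimen itself. Section 14.4 counts any noncompliance with the protocol as a deviation, so, read literally, every participant departs from one section or the other.

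The HIV point is weaker. A figure in Section 6.2 and the study schematic are not shown, and the sentence in 5.3.1 opens with stratified randomization, so its dosing phrase may be loose wording for stratification. It therefore stands only as a cross-reference to be cleared up.

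**Conclusion.** The concern holds. Sections 4 and 6.2 give incompatible regimens in both arms: 3.0-fold apart in daily dose on Days 1-3, 2.0-fold from Day 4, about 2.2-fold in cumulative planned dose before the nominal Day 14 trough, and 2.07-fold through Day 42. The figures assume one strength per product, Section 4 read as written, and no dose modification. The inconsistency is in absolute dose and not in the relation between arms. It must be fixed because the assigned dose underlies participant safety and both Stage I primary outcomes. The HIV wording is a secondary, unreconciled cross-reference. Nothing here indicates which dose or rule is right.

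**What to change.** Reconcile Sections 4 and 6.2 so that both state, in identical words, one regimen per arm: milligrams per dose, capsules per dose, doses per day, and whether Days 1-3 differ. Confirm that the Manual of Procedures and the dispensing and labelling instructions agree with it. Reconcile the HIV phrase and cross-reference in Section 5.3.1 with Section 6.2 and with the stratification statement in the Protocol Summary. The choice of dose and of any HIV-specific rule rests with the sponsor and investigators.

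The cost is a short protocol amendment and a clarification to sites. The design does not change.

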5 STUDY ENROLLMENT AND WITHDRAWAL

5.1 Subject Inclusion Criteria

Subjects must meet all the inclusion criteria in order to be eligible to participate in the study as listed below:

- 1. Male and female patients age > 18 years who have given written informed consent to participate.
- 2. Patients who are unresponsive, critically ill, or requiring sedation so they are cognitively impaired will be considered unable to consent for themselves. A Legally Authorized Representative (LAR) will be approached for informed consent. LAR will be determined using this order: (a) legally appointed guardian, (b) health care proxy or authorized individual to make medical decisions in conjunction with a durable power of attorney, (c) spouse, (d) adult child, (e) parent, or (f) next of kin. Qualification of the LAR will be obtained through verbal assurance from the LAR.
- 3. Patients with a proven or probable endemic mycosis (*Histoplasma*, *Coccidioides*, *Paracoccidioides*, *Blastomyces*, *Sporothrix*, *Talaromyces marneffei* (formerly *Penicillium marneffei*) according to current EORTC/MSG criteria, including patients who:
 - Are immunosuppressed, including as a result of HIV/AIDS
 - Have had a heart, lung or bone marrow transplant
 - Have had chemotherapy for cancer
 - Are otherwise normal hosts

5.2 Subject Exclusion Criteria

All subjects meeting any of these listed exclusion criteria at baseline will be excluded from study participation:

- 1. Significant liver dysfunction as evidenced by at least 5 times greater than upper limits of normal baseline ALT, AST, alkaline phosphatase, or total bilirubin.
- 2. Use of an alternative antifungal therapy (IV or oral) for more than 14 days for this infection with the exception of Coccidioidomycosis. Subjects with Coccidioidomycosis who previously received fluconazole therapy for more than 14 days may be included, if in the opinion of the investigator, they are having an inadequate response or, are intolerant of fluconazole (e.g. due to adverse events). Such subjects must washout from fluconazole for 7 days (~5 half-lives of fluconazole) before starting investigational therapy.
- 3. Evidence of CNS infection.
- 4. Unable to take PO medications.
- 5. Female subjects who are lactating or pregnant.

- 6. Female subjects should be:
 - a) Postmenopausal for 1 year,
 - b) Post-hysterectomy or bilateral oophorectomy,
 - c) If of child bearing potential have a negative β-HCG at screening and using highly effective method of birth control throughout course of study or remain abstinent for duration of study.
- 7. Male subjects with female partner(s) of child-bearing potential, must agree to use a medically acceptable method of contraception during the study. If their partner is pregnant, males must agree to use a condom; if their partner is of child-bearing potential, their partner must additionally be using one of the following methods: hormonal contraception, intra-uterine device, diaphragm, or cervical cap. Spermicides alone are not an acceptable method of contraception. No sperm donations for 90 days post last dose of study therapy.
- 8. Documented intolerance, allergy or hypersensitivity to an azole.
- 9. Inability to comply with study treatment, study visits, and study procedures.
- 10. Known history of congestive cardiac failure on medical treatment, fungal endocarditis, or other causes of ventricular dysfunction that may outweigh the benefit of itraconazole.
- 11. Patients with active TB
- 12. Concurrent use of astemizole, rifampin/rifampicin, rifabutin, ergot alkaloids, long acting barbiturates, carbamazepine, pimozide, quinidine, neostigmine, terfenadine, ketoconazole, valproic acid, or St. John's wort in the 5 days prior to first administration of study drug.
- 13. Any known or suspected condition of the patient that may jeopardize adherence to the protocol requirements or impede the accurate measurement of efficacy.
- 14. Treatment with any investigational agent in the 30 days prior to study entry.
- 15. Patients unlikely to survive 30 days (including severe fungal disease defined by SBP < 90mmHG; hypoxia < 60% saturation).
- 16. Patients with body weight < 40 kg.

